#### **11.4.1.2. Suspected Unexpected Serious Adverse Reactions**

All SUSARs will be handled by appropriate Sponsor (or designee) personnel and reported within the required timelines, in an unblinded fashion, to regulatory authorities and the IRB/IEC, per ICH and local regulations and/or the requirements of the concerned competent authorities.

#### **11.4.2. Reporting Special Situations**

Regardless of whether or not there is an associated AE, special situations will be collected as part of the study drug dosing information and/or as a protocol violation, as required.

Any AEs associated with the special situations should be recorded on the AE eCRF with the diagnosis of the AE.

##### **11.4.2.1. Overdose**

Refer to Section 9.7 for the definition of treatment overdose. An overdose is not an AE. An overdose will be reported even if it does not result in an AE. An overdose will be recorded on the Clinical Trial Safety Reporting Form and sent to the Sponsor or designee within 24 hours according to the process for reporting SAEs (Section 11.4.1).

##### **11.4.2.2. Medication Error**

Any medication error is to be reported to the Sponsor on the Clinical Trial Safety Reporting Form within 24 hours of awareness of the error even if the error does not result in an AE, according to the process for reporting SAEs (Section 11.4.1).

##### **11.4.2.3. Accidental/Occupational Exposure**

Any accidental/occupational exposure (Section 11.1.5) is to be reported to the Sponsor on the Clinical Trial Safety Reporting Form within 24 hours of becoming aware, according to the process for reporting SAEs (Section 11.4.1).

##### **11.4.2.4. Product Misuse/Abuse**

Any misuse/abuse (Section 11.1.5) are to be reported to the Sponsor on the Clinical Trial Safety Reporting Form within 24 hours of becoming aware, according to the process for reporting SAEs (Section 11.4.1).

##### **11.4.2.5. Adverse Events of Special Interest**

All AESIs are immediately reportable events, even if the events do not meet SAE criteria. This includes the events below that are based on laboratory abnormalities, which should be translated to the appropriate AE term at the time of reporting.

All AESIs should be reported to the Sponsor or designee within 24 hours of the Investigator's first knowledge of the event, whether or not the event is serious, even if the experience does not appear to be related to the study drug. AESIs should be reported as described above for SAEs, according to the process for reporting SAEs (Section 11.4.1).

In this study, the following AEs are considered AESIs:

Hepatotoxicity

CCI [Redacted]

Myositis

CCI [Redacted]

Thrombotic microangiopathy (TMA)

CCI [Redacted]

Hypersensitivity

CCI [Redacted]

Thrombocytopenia

CCI [Redacted]

Rhabdomyolysis

CCI [Redacted]

Troponin elevations

CCI [Redacted]

### **11.4.3. Miscellaneous**

#### **11.4.3.1. Responsibilities of the Investigator**

The responsibilities of the Investigator related to safety reporting include, but are not limited to, the following:

- Monitoring and recording all AEs
- Determining the seriousness, severity, and relationship to study drug, study procedure, and underlying disease for each AE
- Determining the onset and end date of each AE
- Providing the initial report of all SAEs, special situations, and noted AESIs to the Sponsor via email to PPD or designee within 24 hours of first knowledge.
- Providing follow-up information on SAEs in a timely and proactive manner
- Responding to queries regarding AEs and SAEs in a timely manner
- Ensuring that source documentation for all AEs is accurate and complete
- Ensuring that the study is conducted as defined in this protocol
- Submission of safety events to the IEC/IRB according to the policies and requirements

Investigators may also report improvement of pre-existing DMD conditions or unexpected therapeutic responses.

#### **11.4.3.2. Responsibilities of the Sponsor**

The responsibilities of the Sponsor related to safety reporting include, but are not limited to, the following:

- Training of Investigator on AE/SAE, special situations and AESI definitions, safety assessments, and site obligations related to safety monitoring and reporting of AEs/SAEs
- Training with regard to the accurate and legal reporting of SAEs to all applicable regulatory authorities, IRBs/IECs, clinical study sites, and other parties, as appropriate and required within the regulated timing
- Ensuring accurate recording of AEs and SAEs, Special Situations, and AESIs
- Submission of expedited serious, unexpected, and related AEs to regulatory authorities per regulatory requirements
- Notification of blinded, unexpected and related SAEs to sites
- Annual safety reporting to regulatory authorities and IRBs/IECs according to regional requirements

## 12. STATISTICAL CONSIDERATIONS

### 12.1. Statistical Hypotheses

For the primary efficacy endpoint of change in NSAA total score from Baseline to Week 52 (Part 1), the null hypothesis is that the population means for the 2 treatments are equal and the alternative hypothesis is that the population means for the 2 treatments are not equal. Even though the alternative hypothesis is 2-sided, only superiority of delandistrogene moxeparvec over placebo will be of interest.

The statistical hypotheses for secondary efficacy endpoints can be stated in a similar manner as those for change in NSAA total score from Baseline to Week 52 (Part 1).

### 12.2. Sample Size Determination

The sample size of this study is based on the power for the primary efficacy endpoint, change in NSAA total score from Baseline to Week 52 (Part 1).

CCI [REDACTED]  
[REDACTED]  
[REDACTED]  
[REDACTED]  
[REDACTED]

This sample size calculation CCI [REDACTED] is based on efficacy data from a double-blind, placebo-controlled, Phase 2 study as well as comparison against external controls in DMD.

### 12.3. Analysis Populations

For purposes of statistical analyses, the following analysis populations are defined:

| Population                      | Description   |
|---------------------------------|---|
| Intent-to-Treat (ITT)           | All randomized subjects (not including those enrolled under a regional addendum), with treatment group designated according to randomization.   |
| Modified Intent-to-Treat (mITT) | All randomized subjects who receive study treatment (not including those enrolled under a regional addendum), with treatment group designated according to randomization. The mITT population will be the analysis population for efficacy endpoints. |
| Safety                          | All subjects who received study treatment (not including those enrolled under a regional addendum), with treatment group designated according to the treatment that they actually received.   |

## **12.4. Statistical Analyses**

This section is a summary of the planned statistical analyses of the primary and secondary efficacy endpoints as well as the safety analyses. Details of the statistical analyses will be included in the SAP, which will be developed and finalized before database lock and unblinding of the study data.

### **12.4.1. Subject Disposition**

The number and percentage of subjects completing or prematurely discontinuing from the study will be summarized by treatment. Reasons for premature discontinuation will also be summarized. The analyses will be based on the mITT population.

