### **8.3. Screen Failures**

Screen failures are defined as subjects who consent to participate in the clinical study but are not subsequently randomly assigned to study drug. A minimal set of screen failure information including demography, screen failure details, eligibility criteria, and any SAE information are required to ensure transparent reporting of screen failure subjects. CCI [REDACTED]

Individuals who do not meet the criteria for participation in this study (screen failure) may be re-screened at the Investigator's discretion with Sponsor approval.

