### **8.5. Subject Withdrawal Criteria**

Any subject can decide to withdraw from study participation at any time for any reason. A subject who withdraws prior to dosing may be replaced at the discretion of the Sponsor. In addition, the Sponsor may decide to stop the study participation of any subject as deemed necessary. The Investigator may also stop the study participation of any subject at any time. Reasons for withdrawal from the study include, but are not limited to:

- The subject or parent(s)/legal guardian(s) withdraws consent.
- Prior to randomization and dosing it is determined that the subject was erroneously included in the study (ie, was found to not have met the eligibility criteria).
- The subject is unable to comply with the requirements of the protocol.
- The subject participates in another investigational study without prior written authorization of the Sponsor.

The Investigator or study staff will document the reason(s) for withdrawal on the electronic case report form (eCRF). If withdrawn subjects received study drug, every effort should be made to request that the subject allow follow-up for safety purposes.

Subjects who withdraw from the study must return the wearable device.

Subjects who have received study drug and withdraw from the study but do not withdraw consent will be asked to continue telephone calls to collect AEs and concomitant medications and have blood collected for laboratory assessments according to Section 2.3 CCI [REDACTED] after infusion (if subjects withdraw within this window), and then for

safety laboratory assessments approximately CCI starting from the date of the last safety laboratory assessment before withdrawal. For this study, safety laboratory assessments include the following: electrolytes, troponin, liver function, hematology, high-sensitivity C-reactive protein (hsCRP) and complement, renal function, and urinalysis (see Section 10.4.6.1 for a list of analytes associated with each parameter).

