#### **9.3.2. Blinding/Unblinding**

##### **9.3.2.1. Blinded and Unblinded Personnel**

All subjects, parents/caregivers, Investigators, and site staff with the exception of the unblinded site pharmacist will be blinded to the treatment the subject receives (delandistrogene moxeparovec or placebo). The unblinded pharmacist (or designee) will perform drug preparation according to the randomized treatment assigned. All documentation of study drug preparation will be maintained in a secure location which prevents access or disclosure to all blinded clinical study personnel. Refer to the study blinding plan for further details.

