## 11.2. Collection of Adverse Events

All AEs, regardless of the source of identification (eg, physical examination, laboratory assessment, ECG, reported by subject), must be collected, and documented in the eCRF.

All AEs will be collected and recorded from the time of informed consent/assent through the last follow-up visit.

All AEs (including AESIs and special situations) and SAEs experienced by a subject, irrespective of the suspected causality, will be monitored until the AE or SAE has resolved, any abnormal laboratory values have returned to stabilization, baseline status, and there is a satisfactory explanation for the changes observed, completion of the subject's study participation, or study termination, whichever occurs first.

Concomitant illnesses that existed before entry into the study will not be considered AEs unless the illness worsens during the treatment period. Pre-existing conditions must be recorded in the eCRF, as well as on the Clinical Trial Safety Reporting Form's medical history section.

For subjects who are prematurely discontinued from the study (Section 8.5), AEs should continue to be recorded at least until 28 days after the last study drug administration.

For subjects who are found to be ineligible for the study during the Pre-infusion Period and are not enrolled (ie, screen failures), only SAEs (Section 11.1.2) will be reported (Section 11.4.1).

If, at any time after the subject has completed participation in the study (Section 8.4), the Investigator or study staff become aware of an SAE that the Investigator assesses as related to the study drug (Section 11.3.1) or related to a study procedure (Section 11.3.2), then the event and any known details must be reported promptly to the Sponsor, no later than within 24 hours of awareness.

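### Does basing the disposition summary on mITT lose sight of boys who are randomised but never infused?

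*Combined protocol and SAP*

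**What the plan says.** Section 12.4.1 of the protocol plans a by-treatment summary of how many subjects finish the study and how many leave early. It adds: "Reasons for premature discontinuation will also be summarized. The analyses will be based on the mITT population".

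Section 12.3 defines the two sets that matter here. ITT is "All randomized subjects (not including those enrolled under a regional addendum), with treatment group designated according to randomization". mITT is narrower: "All randomized subjects who receive study treatment (not including those enrolled under a regional addendum"), again grouped as randomised. Section 12.3 also makes mITT the efficacy set. Sections 12.4.2 and 12.4.3 use mITT for baseline characteristics and concomitant medications, and section 12.4.5.1 uses the safety population for safety.

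Other sections bear on a boy who stops between randomisation and infusion:

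- Section 8.3: "Screen failures are defined as subjects who consent to participate in the clinical study but are not subsequently randomly assigned to study drug".
- Section 8.5: "A subject who withdraws prior to dosing may be replaced at the discretion of the Sponsor". The same section states: "The Investigator or study staff will document the reason(s) for withdrawal on the electronic case report form (eCRF").
- Section 9.3.2.1: "The unblinded pharmacist (or designee) will perform drug preparation according to the randomized treatment assigned".
- Section 11.2, on event reporting: "For subjects who are found to be ineligible for the study during the Pre-infusion Period and are not enrolled (ie, screen failures), only SAEs" are reported.

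Section 12.4 presents itself as an outline and refers the detail to the SAP.

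**The concern.** Efficacy is analysed on mITT, so a reader will want to know how many randomised boys are missing from that set, from which arm and why. The disposition summary is the natural place to look. If it is built on the same set, its denominator starts after those losses and it cannot show them.

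Such a boy is also not a screen failure, because section 8.3 ends that category at random assignment. Section 11.2 is worded more loosely, but it governs which events are reported and does not clearly reach a family that withdraws consent after randomisation. He is left in ITT only, and no analysis in the unredacted text of section 12 is assigned to ITT.

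Replacement could hide the loss further. If each boy lost before dosing is replaced, the treated total still reaches about 120 and nothing in the summary shows that more were randomised. At stake is transparent reporting of attrition. Bias in the primary comparison is a separate question, which the disposition denominator does not affect.

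**Working it through.** **Step 1: place the boy in each set.** The plan states no figure on this point, so there is none to reproduce. The definitions settle where he belongs.

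| Set | Section | Requires | Randomised, never infused |
|---|---|---|---|
| Screen failure | 8.3 | consented, not randomised | out |
| ITT | 12.3 | randomised | in |
| mITT | 12.3 | randomised and treated | out |
| Safety | 12.3 | treated | out |

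A placebo infusion counts as study treatment. A boy infused in Part 1 who does not go on to the Part 2 infusion therefore stays in mITT, and the issue is confined to losses before the first infusion.

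**Step 2: can the case arise?** Drug is prepared to the randomised assignment (section 9.3.2.1), so randomisation precedes infusion. Section 8.5 foresees withdrawal before dosing but does not say whether it means before or after randomisation. The case is possible. Its frequency is not given.

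**Step 3: size.** Let k be the number randomised but never infused; k is an assumption throughout. The synopsis plans about 120 enrolled, and section 7.1.2 expects about 60 + 60 = 120 infused. Two readings follow:

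- 120 randomised, no replacement: share omitted = k/120.
- 120 infused, every loss replaced: share omitted = k/(120 + k).

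| k | k/120 | k/(120 + k) |
|---|---|---|
| 0 | 0% | 0% |
| 1 | 1/120 = 0.8% | 1/121 = 0.8% |
| 2 | 2/120 = 1.7% | 2/122 = 1.6% |
| 3 | 3/120 = 2.5% | 3/123 = 2.4% |
| 6 | 6/120 = 5.0% | 6/126 = 4.8% |

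**Step 4: effect on the reported discontinuation rate.** Suppose, again by assumption, that 3 infused boys also leave early, with 120 randomised and no replacement. The mITT rate is 3/(120 − k) and the all-randomised rate is (3 + k)/120.

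| k | On mITT | On all randomised |
|---|---|---|
| 1 | 3/119 = 2.5% | 4/120 = 3.3% |
| 3 | 3/117 = 2.6% | 6/120 = 5.0% |
| 6 | 3/114 = 2.6% | 9/120 = 7.5% |

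The mITT rate barely moves, while the all-randomised rate rises with k. With k = 0 the two are identical.

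**Step 5: what else would change?** The efficacy set is fixed by section 12.3 and the safety set by sections 12.3 and 12.4.5.1. Neither depends on the disposition denominator. A different denominator in section 12.4.1 would leave the primary model, the hierarchical testing and the safety tables as they are.

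**The case for a change.** The best case for acting is that section 12.4.1 does not leave the population open. It names mITT, so a SAP that put disposition on ITT would depart from the protocol's wording, and aligning the two would cost one table line and a few words. The event is also realistic. Some exclusions in section 8.2, such as recent major surgery or a symptomatic infection, are timed to Day 1, so a boy could become ineligible after assignment. And section 8.3 takes care to keep minimal information on screen failures, while the protocol names no reporting line for a boy who got further.

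Much of this stands. The reading of the definitions is correct, and showing everyone randomised is better reporting. But the wording does not exclude a further table or line, so adding a count of boys randomised and not treated contradicts nothing in section 12.4.1. The absence of any visible use of ITT is weak evidence: the set is defined, the SAP text was not available for this check, and parts of section 12.4.4.1 are redacted. Being outside the screen-failure category is simply what follows from having been randomised. It is not a second gap. The information is not lost either, since assignment is made through the IRT (section 9.3.1) and the reason for withdrawal goes on the eCRF (section 8.5).

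**Conclusion.** The observation is accurate, but no change to the plan is needed. Read literally, section 12.4.1 would omit any boy randomised and never infused. With 1 to 3 such boys, that is 0.8% to 2.5% of 120 randomised, or 0.8% to 2.4% if each is replaced; with none it is zero. These figures rest on an assumed k and on taking the planned number of about 120 as exact.

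The consequence stops at the completeness of one descriptive table. No estimate, test, decision or safety conclusion turns on it. It is a gap in a short outline that trial analysts ordinarily fill when they account for all randomised subjects in the SAP and the study report, and the data needed are already collected. This conclusion does not assume that the SAP already contains the line; it rests on the small consequence and on the line being easy to produce. A large or lopsided number of untreated boys would deserve comment in the study report, but nothing in the documents points to one.

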### **12.4.2. Demographic and Baseline Characteristics**

Demographic information and baseline characteristics including age (years), sex at birth, race, ethnicity, baseline height (cm), weight (kg), body mass index ( $\text{kg}/\text{m}^2$ ), genetic mutations, and prognostic factors such as baseline measures for functional assessments will be summarized by treatment. The analyses will be based on the mITT population.

### **12.4.3. Concomitant Medications**

Concomitant medications will be coded by preferred term (PT) using the most recent World Health Organization Drug Dictionary (WHODrug) version. The number and percentage of subjects in the mITT population with concomitant medications will be tabulated by Anatomical Therapeutic Chemical classification pharmacological subgroup and WHODrug PT.

### **12.4.4. Efficacy Analyses**

The primary endpoint and some secondary endpoints will be tested in a hierarchical manner using an appropriate multiple testing approach that provides strong control of the familywise Type 1 error rate at a 2-sided 0.05 level. The details of the testing procedure will be specified in the SAP.

#### **12.4.4.1. Analyses of Primary Efficacy Endpoint**

For the primary endpoint of change in NSAA total score from Baseline to Week 52 (Part 1), summary statistics will be provided by treatment group for NSAA total score at Baseline, each post-Baseline visit in Part 1, and for change from Baseline to each post-Baseline visit in Part 1.

CCI

As the primary analysis, a restricted maximum likelihood-based mixed model repeated measures analysis will be used to compare the 2 treatment groups for change in NSAA total score from Baseline to Week 52 (Part 1). In this model, the response vector consists of the change in NSAA total score from Baseline to each post-Baseline visit in Part 1. The model will include the covariates of treatment group (categorical), visit (categorical), treatment group by visit interaction, age group at randomization, baseline NSAA total score, age group at the time of randomization by visit interaction, and baseline NSAA total score by visit interaction. All covariates will be fixed effects in this analysis.

An unstructured covariance matrix will be used to model the within-subject variance-covariance errors. If the unstructured covariance structure results in a lack of convergence, the heterogeneous first-order autoregressive covariance structure will be used. The Kenward-Roger approximation will be used to estimate the denominator degrees of freedom (Kenward 1997). In the primary analysis, missing data are assumed to be missing at random.

Sensitivity analyses will be performed to assess the robustness of the primary analysis conclusions with respect to deviations from missing at random assumption.

CCI

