| 
CCI [REDACTED]
[REDACTED]
[REDACTED]
[REDACTED]
 
This sample size calculation CCI [REDACTED] is based on efficacy data from a double-blind, placebo-controlled, Phase 2 study as well as comparison against external controls in DMD.
 
Efficacy Analyses:
The primary endpoint and some secondary endpoints will be tested in a hierarchical manner using an appropriate multiple-testing approach that provides strong control of the familywise Type 1 error rate at a 2-sided 0.05 level. The details of the testing procedure will be specified in the statistical analysis plan (SAP).
For the primary endpoint of change in NSAA total score from Baseline to Week 52 (Part 1), summary statistics will be provided by treatment group for NSAA total score at Baseline, each post-Baseline visit in Part 1, and for change from Baseline to each post-Baseline visit in Part 1. CCI [REDACTED]
[REDACTED]
 
As the primary analysis, a restricted maximum likelihood-based mixed model repeated measures analysis will be used to compare the 2 treatment groups for change in NSAA total score from Baseline to Week 52 (Part 1). In this model, the response vector consists of the change from Baseline in NSAA total score at each post-Baseline visit in Part 1. The model will include the covariates of treatment group (categorical), visit (categorical), treatment group by visit interaction, age group at randomization (categorical), age group at randomization by visit interaction, Baseline NSAA total score, and Baseline NSAA total score by visit interaction. All covariates will be fixed effects in this analysis.
An unstructured covariance matrix will be used to model the within-subject variance-covariance errors. If the unstructured covariance structure results in a lack of convergence, the heterogeneous first-order autoregressive covariance structure will be used. The Kenward-Roger approximation will be used to estimate the denominator degrees of freedom. In the primary analysis, missing data are assumed to be missing at random.
The superiority of delandistrogene moxeparovec over placebo will be concluded if the test achieves statistical significance based on the multiplicity-adjusted testing procedure that will be specified in the SAP.
 
Interim Analysis: The primary analysis of the study will be performed after all subjects have completed Part 1 or have withdrawn early from Part 1. No interim analysis is planned prior to the completion of Part 1.
 
Data Monitoring Committee: A program-wide independent Data Monitoring Committee (DMC) will monitor safety, efficacy, data quality, and the integrity of study. The activities and composition of this committee are outlined in the DMC Charter.
 |   |

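### If the heterogeneous AR(1) fallback is used with model-based Kenward-Roger inference, the Week 52 standard error is likely to be modestly too small; naming a bias-corrected sandwich standard error would repair this cheaply

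*Combined protocol and SAP*

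**What the plan says.** Protocol Section 12.4.4.1 specifies that "a restricted maximum likelihood-based mixed model repeated measures analysis will be used to compare the 2 treatment groups". Treatment, age group and baseline NSAA are each crossed with visit; the last two terms listed are "age group at the time of randomization by visit interaction, and baseline NSAA total score by visit interaction". On covariance: "An unstructured covariance matrix will be used to model the within-subject variance-covariance errors". The only fallback is: "If the unstructured covariance structure results in a lack of convergence, the heterogeneous first-order autoregressive covariance structure will be used". The Synopsis (Section 2.1) repeats it: "the heterogeneous first-order autoregressive covariance structure will be used". For inference, "The Kenward-Roger approximation will be used to estimate the denominator degrees of freedom".

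The one sensitivity analysis described concerns missing data: "Sensitivity analyses will be performed to assess the robustness of the primary analysis conclusions with respect to deviations from missing at random assumption". Section 12.4.4 promises "strong control of the familywise Type 1 error rate at a 2-sided 0.05 level" for the testing procedure. Section 12.4 leaves detail to a SAP to be finalized before database lock and unblinding. Section 12.4.4.2 carries similar methods, as appropriate, to most secondary endpoints. The readable text names no sandwich variance, retry step or intermediate covariance structure.

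**The concern.** Kenward-Roger allows for the covariance parameters being estimated. It does not protect against the wrong structure. Heterogeneous AR(1) gives each visit its own variance, so one might expect the Week 52 variance to be estimated freely. It is not: one correlation parameter has to serve every pair of neighbouring visits. When boys differ in rate of progression, neighbouring correlations rise through follow-up, and the likelihood compensates partly by shrinking the variance at the last visit, where the primary test is made.

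The p-value and confidence interval would then be somewhat optimistic on the fallback path, in favour of declaring efficacy. If the problem were noticed only after unblinding, a switch to a robust standard error would look post hoc.

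**Working it through.** **Inputs from the documents.** About 120 boys (Section 7.1), randomized 1:1 (9.3.1); two-sided 0.05 (12.4.4); mean and covariance model (12.4.4.1).

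**Assumed, because redacted.** Visit schedule (7.1.3) and standard deviations (12.2). I used 2, 3, 4, 5 or 7 post-baseline visits, between-boy slope SD 0 to 4 NSAA points per year, visit error SD 1 to 2 points and intercept SD 3.5 points.

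**Step 1: the plan's 5% under its first-choice model.** Simulation with 60 per arm, visits at Weeks 12, 24, 36 and 52, error SD 1.5, complete data, 4,000 trials and t on 116 df gave 5.03%, 4.90% and 5.03% at slope SD 0, 2 and 3. Monte Carlo SE is √(0.05 × 0.95 / 4000) = 0.34 points. The stated 5% is reproduced.

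**Step 2: why AR(1) differs.** Because every covariate is crossed with visit, with complete data the Week 52 estimate is the same under any covariance; only its SE changes. Conditional on baseline, the covariance of visits j and k (times t in years) is

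S(j,k) = c + σs² t(j) t(k) + σe² [if j = k], where c = 3.5² − (3.5²)² / (3.5² + 1.5²) = 12.25 − 150.06/14.5 = 1.90.

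With slope SD 2 and error SD 1.5, the true Week 52 variance is 1.90 + 4 + 2.25 = 8.15, and the neighbouring-visit correlations are 0.498, 0.577 and 0.664. The large-sample AR(1) fit V minimises log|V| + tr(V⁻¹S). V⁻¹ is tridiagonal, so only the variances and neighbouring covariances enter. The solution has a common correlation of 0.583 and a Week 52 variance of 7.62.

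- SE ratio = √(7.62/8.15) = 0.967; type I error = 2[1 − Φ(1.96 × 0.967)] = 5.8%.
- Slope SD 3: variances 11.72 against 13.15, ratio 0.944, type I error 6.4%.
- Slope SD 0: all neighbouring correlations are 0.458, ratio 1.000, type I error 5.0%. The true correlation three visits apart is also 0.458 against a fitted 0.458³ = 0.096. Geometric decay alone is therefore not the cause; unequal neighbouring correlations are.
- Two visits: AR(1) has two variances and one correlation, exactly the unstructured matrix, so 5.0%.

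**Step 3: range over assumptions** (large sample; 288 covariances per schedule, with slope SD 1.5 to 4, varying intercept-slope correlation and an optional serial process).

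| Post-baseline visits | SE ratio | Type I error: min / median / max |
|---|---|---|
| 2 | 1.000 | 5.0 / 5.0 / 5.0% |
| 3 | 0.957–1.008 | 4.8 / 5.3 / 6.1% |
| 4 | 0.912–0.996 | 5.1 / 5.9 / 7.4% |
| 5 | 0.866–0.992 | 5.2 / 6.4 / 9.0% |
| 7 | 0.824–0.984 | 5.4 / 7.1 / 10.6% |

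With three visits, 91% of cases exceed 5%, mostly slightly. A separate check with narrower assumptions gave 5.3–5.9%, 5.6–7.0% and 5.7–8.1% for three, four and five visits.

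**Step 4: complete-data simulation.** In the Step 1 setting, AR(1) gave 5.05%, 5.75% and 6.20% at slope SD 0, 2 and 3. A sandwich SE with leverage-corrected residuals gave 4.80%, 4.57% and 4.60%. A second set (3,000 trials per scenario; five of eight planned scenarios completed) gave AR(1) 6.0–7.3%, unstructured 4.6–5.7% and sandwich 4.5–5.7%.

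**Step 5: with dropout** (four visits, missing at random).

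- About 11–15% dropout, 1,081 to 1,325 runs per scenario, Monte Carlo SE 0.6 to 0.8 points. AR(1) gave 7.96% (slope SD 3, error SD 1.5; mean SE 0.660 against empirical SD 0.703), 6.72% (3 and 1; 0.579 against 0.625) and 4.56% (2 and 1.5; 0.530 against 0.531).
- About 15% dropout, three scenarios, 1,500 runs each, Monte Carlo SE about 0.6 points. AR(1) gave 5.7%, 6.2% and 6.9%; an uncorrected sandwich 5.7–5.9%; a bias-corrected sandwich 4.5–5.2%.

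The simulations in Steps 1 and 4 and the first set in Step 5 used fixed t degrees of freedom as a stand-in for Kenward-Roger.

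**The case against.** The strongest reply is that this path will hardly ever be taken. With complete data and all covariates crossed with visit, the unstructured estimate has a closed form, and about 120 boys with few visits give little reason for failure. If the fallback had an assumed 1% to 5% chance of use and a 7.3% error rate when used, the overall rate would be 0.01 × 7.3 + 0.99 × 5 = 5.02% to 0.05 × 7.3 + 0.95 × 5 = 5.12%. That stands, and it is why the severity is low. It does not remove the reason to write the fallback well: it matters only when it is used, and then it is the confirmatory analysis.

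Second, the inputs are redacted, and one of the three scenarios in the first dropout set showed no inflation. That also stands. The direction is likely, not certain, and the size is conditional.

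Third, the SAP text is not supplied and parts of Section 12.4.4.1 are redacted, so a robust variance may be specified there. Its absence is a statement about the readable text only.

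Fourth, a sandwich is not automatically a cure. In a further run of 822 trials (slope SD 2, error SD 1.5, about 15% dropout), an uncorrected sandwich gave 5.7% against 6.1% for AR(1) and 5.2% for unstructured. Its mean SE was 0.547 against an empirical SD of 0.575, so still about 5% short (0.547/0.575 = 0.951). These rates are too close to separate given the Monte Carlo error, but the shortfall is reason not to rely on the uncorrected form. The bias-corrected form held its level in the larger runs.

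**Conclusion.** The point holds as a conditional, low-severity one. If the unstructured fit fails and AR(1) is used with model-based Kenward-Roger inference, the Week 52 standard error is likely to be modestly too small when there are at least three post-baseline visits and boys' slopes vary. Under the assumed variances, type I error is about 5–6% with three visits, 5.5–7% with four, and up to about 8% or somewhat more with five or more. The values of 9% to 10.6% in the table are large-sample extremes with many visits. With two visits, or no slope variation, there is no inflation.

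A reader might infer that the primary test breaks its 5% level, or that the strong-control statement in Section 12.4.4 is false. The documents do not support that. The first-choice model holds its level and probably converges, and the Section 12.4.4 statement describes the multiplicity procedure, which is not at fault here. Nor do the documents show that AR(1) is wrong for NSAA data: they give no NSAA correlations, and variation in slope is an assumption, plausible for boys aged 4 to under 8 with a progressive disease.

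**What to change.** In Section 12.4.4.1, the Synopsis and the SAP, replace the single-step fallback with a fixed sequence:

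1. On non-convergence, refit the unstructured matrix with a pre-stated set of alternative starting values or a pre-stated alternative algorithm.
2. If AR(1) is still needed, base the Week 52 test and interval on one named bias-corrected sandwich standard error, clustered by boy, with one named degrees-of-freedom method, instead of Kenward-Roger. One candidate is the leverage-corrected form with residual degrees of freedom, as checked on complete data in Step 4. An uncorrected sandwich should not be relied on at this sample size.

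Step 1 should come first because a sandwich repairs the standard error but not any bias in the estimate from a wrong covariance under dropout.

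Apply the same rule to the secondary endpoints that use this model. Their error rates were not calculated here. Dystrophin expression is outside this, since Section 12.4.4.2 gives it a re-randomization test.

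Cost: one or two sentences before database lock and unblinding, and a slightly wider interval on the fallback path only. Nothing changes if the unstructured model converges.
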